## 1. Study Summary

Study Title	Randomized Controlled Trial To assess the Benefits of Dexcom Continuous Glucose Monitoring with Glucose telemetry System for the Management of Diabetes in Long-term Care Setting: The CGM-GTS in Long-term care
Study Design	Randomized Controlled Trial
Primary Objective	To compare differences in frequency of hypoglycemia (<70 mg/dl) and glycemic control (time in range [TIR] 80-180 mg/dl) between the Dexcom CGM with Glucose Telemetry System (CGM-GTS) compared to a standard of care protocol, in residents with T2D treated with insulin and/or insulin-secretagogues, in subacute and long-term skilled nursing care facilities.
Secondary Objective(s)	Determine differences in clinical outcomes (number of complications, ER visits and need for hospital re-admissions), and health care utilization between the use of real-time Dexcom CGM Glucose Telemetry System (CGM-GTS) compared to a standard of care in patients with T2D in subacute and long-term skilled nursing care facilities.
Research Intervention(s)/Interactions	POC testing or to real time Dexcom CGM with GTS for up to 60 days of admission.
Study Population	Adult residents with T2D in subacute and long-term skilled nursing care facilities treated residents with T2D treated with insulin and/or insulin-secretagogues.
Sample Size	100
Study Duration for individual participants	Length of admission to subacute and long-term skilled nursing care facilities or up to 60 days (whichever comes sooner)
Study Specific Abbreviations/ Definitions	T2DM: Type 2 Diabetes Mellitus OADs: oral antidiabetic medications CGM: continuous glucose monitor GTS: glucose telemetry system LTC: Long Term Care SSI: Sliding Scale Insulin
Funding Source (if any)	Dexcom, Inc.

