## 9. Study Timelines

The duration of an individual participant's participation in the study will be equal the length of admission to subacute and long-term skilled nursing care facilities (LTC) or up to sixty (60) days, whichever comes sooner.

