### Inclusion Criteria:

1. Males and females admitted to subacute and long-term skilled nursing care facilities
2. Known history of T2D treated with insulin (glargine, detemir, degludec, NPH, premixed insulin) or sliding scale regular insulin) or insulin secretagogues (sulfonylureas, repaglinide, nateglinide) with or without additional oral antidiabetic agents (alpha-glucosidase inhibitors, thiazolidinedione, SGLT2- inhibitors, DPP4-inhibitors), short- and long-acting GLP1-RA (exenatide, liraglutide, dulaglutide, semaglutide)
3. Patients with an expected LTC length-of-stay > 1 week

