The present aims of this RCT is to investigate whether the Dexcom G6 CGM with Glucose Telemetry System (CGM-GTS) with hypoglycemia alarm may reduce the risk of hypoglycemia < 70 mg/dl (safety outcome) and improve glycemic control as measured by the percent of time in range (TIR) 70-180 mg/dl (efficacy end-point) in patients with T2D in subacute and long-term skilled nursing care facilities. Patients in the standard of care group will wear a blinded CGM and receive POC testing before meals and bedtime, with providers adjusting oral agents or insulin dose based on POC results. Patients in the intervention CGM group will have a single daily fasting POC testing and will wear a real-time Dexcom G6 with GTS, and providers will adjust oral or insulin therapy based on CGM-GTS profile information. [name], PhD at the School of Public Health at Emory University will conduct statistical analyses.

For the safety endpoint, we will first compare the proportions of patients who have at least one episode of hypoglycemia by POC and by CGM. We will first perform nonparametric comparisons of the rate of hypoglycemia based on a two-sided Chi-square test (or Fisher's exact test in the presence of low incidence rates), followed by the Cochran-Mantel-Haenszel test, which adjusts for the potential center effect. Then we will perform univariate Poisson regression (or Negative Binomial regression) to assess whether there is any difference in the number of clinically significant hypoglycemia events between the two treatment groups. We will further conduct multivariate Logistic regression, Poisson regression (or Negative Binomial regression) to estimate the difference in the rate and frequency of hypoglycemia while adjusting for potential confounders. A glucose value < 70 mg/dl is considered as hypoglycemia requiring a nurse-driven response; thus, a BG <70 mg/dl will be used for sample size calculation. Data from Singh et al a reduction of hypoglycemia was reported comparing the CGM/GTS system than POC (Singh et al 2020) per patient (0.67 episodes per patient, 95% CI 0.34-1.30

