versus 1.69 episodes per patient, 95% CI 1.11-2.58,  $p= 0.024$ ) . Based on the results of the recent glargine U100 vs U300 study using CGM monitoring in the hospital, 56% had CGM BG readings <70 mg/dl (vs 14% with POC testing-standard of care), it is reasonable to assume 60% of resident on LTC facilities will experience one or more BG < 70 mg/dl by CGM. If we assume that 35% in the standard of care group will have at least one BG <70 mg/dl (based on linagliptin LTC study) , using one-sided, two-sample t-tests, we require we will need 70 patients per group to achieve 80% power.

Hypoglycemia incidence, Rate in the CGM intervention group	30%	35%	40%	45%	50%
Estimated sample size (N/group) for 80% power	49	70	107	186	407

For the efficacy endpoint, we will compare mean daily glucose levels measured by CGM or POC, and percent TIR measured by CGM between treatment groups by nonparametric Wilcoxon-tests or two-sample t-tests, and by multivariate linear regression, which adjusts for other potential confounders such as age, gender, BMI, center, and admission HbA1c. A logarithm transformation may be employed to make the data better conform to the normality assumption. When conducting multivariate regression analyses, we will apply standard variable selection and model checking procedures to decide the final model. Stepwise, backward, or forward model selection strategy will be adopted to determine the variables to be included in the final model. Standard diagnostic and model checking procedures, such as deviance residual plot and Hosmer- Lemeshow test, will be applied to examine the fit of the developed models. To show non-inferiority between POC and CGM in terms of glycemic control, we set the equivalence margin of 18 mg/dl (1 mosm/l), from a view that a difference <18 mg/dl is usually not considered as clinically significant . Based on the results from our recent CGM trials , it is reasonable to assume the standard deviation of mean daily BG is bounded above by 45 mg/dl. Assuming the true BG difference between the treatment groups is zero, and using one-sided, two-sample t-tests, we require 70 subjects for each treatment group to achieve 80% power.

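### The hypoglycaemia count analysis leaves plain Poisson open and names no exposure term, and adjusted models take covariates chosen by automatic selection

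*Combined protocol and SAP*

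**What the plan says.** The statistical text in Section 18 analyses the safety endpoint in stages.

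- **Proportions.** It starts with "nonparametric comparisons of the rate of hypoglycemia based on a two-sided Chi-square test", then a Cochran-Mantel-Haenszel test for centre.
- **Counts.** It then uses "univariate Poisson regression (or Negative Binomial regression) to assess whether there is any difference in the number of clinically significant hypoglycemia events". Clinically significant means below 54 mg/dL (Sections 4 and 15). Numbers of events below 70 and below 54 mg/dL are secondary outcome 2 in Section 4; both thresholds also stand in primary outcome 1.
- **Adjusted models.** Logistic and count models follow, "to estimate the difference in the rate and frequency of hypoglycemia while adjusting for potential confounders". No covariates are listed for these. The efficacy model "adjusts for other potential confounders such as age, gender, BMI, center, and admission HbA1c".
- **Covariate choice.** "Stepwise, backward, or forward model selection strategy will be adopted to determine the variables to be included in the final model". No entry or exit thresholds are given, and nothing says that treatment stays in the model.

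On observed time, Section 9 says that participation will "equal the length of admission to subacute and long-term skilled nursing care facilities (LTC) or up to sixty (60) days, whichever comes sooner". Entry requires only "Patients with an expected LTC length-of-stay > 1 week". Secondary outcome 9 in Section 4 counts sensor removals, failures and dislodgments, so valid CGM time can be shorter than the stay.

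No section names an offset, person-days or wear time. The word *rate* does not supply one, because Section 18 uses it for the proportion tested by chi-square.

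**The concern.** Poisson regression takes the variance of a count to equal its mean. Residents differ in their tendency to hypoglycaemia, so counts vary more than that, standard errors come out too small and chance differences look significant. If the choice between Poisson and negative binomial is made after the data are seen, the error rate of the count comparison is not controlled.

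Without an exposure term, the model estimates the ratio of events per stay. This equals the ratio of events per day only if the arms are observed equally long. Differences in time between residents also add noise.

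Automatic selection leaves the adjusted treatment estimate dependent on a model that nobody can write down in advance.

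**Working it through.** **The plan's own figure.** The plan gives no figure for the count model. Its 70 per group rests on proportions: 60% against 35%, two-sided 5%, 80% power, continuity-corrected, gives 49, 70, 107, 186 and 408 across the table, against the printed 49, 70, 107, 186 and 407. The sample size does not depend on the count model.

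**Inputs**
- 100 participants (Sections 1 and 12); 50 per arm assumes equal allocation.
- Control means of 1.69 events (<70) and 0.75 events (<54) per patient, from the hospital telemetry trial in Section 3. No time denominator is given, so 5, 10 or 30 days is assumed.
- Stay uniform on 7-60 days (assumed): mean 33.5, variance 53²/12 = 234.1, CV² = 234.1/33.5² = 0.209.
- Variance of a count = μ + kμ², with k = 0.8, 1.59 or 3.0 (assumed). The middle value fits 1.69 events and 56% with any event: 1 − (1 + 1.59 × 1.69)^(−1/1.59) = 0.56. Those two figures come from different hospital studies.

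**Is overdispersion plausible?** Section 18 quotes 1.69 (95% CI 1.11-2.58) and 0.67 (0.34-1.30). The first gives SE(log) = ln(2.58/1.11)/3.92 = 0.215. Pure Poisson would need n = 1/(1.69 × 0.215²) = 12.8 patients for that width; the second interval also gives 12.8. The cited trial's size is not in the documents. At 20, 30 or 40 per arm the variance would be 1.6, 2.3 or 3.1 times Poisson.

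**Poisson, no true effect, balanced stay.** The variance inflation is
- with offset: φ = 1 + kμ(1 + CV²)
- without offset: φ = 1 + kμ(1 + CV²) + μCV²

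and the rejection rate is about 2Φ(−1.96/√φ). First row below: μ = 1.69 × 33.5/30 = 1.887, so φ without offset = 1 + 3.627 + 0.394 = 5.02.

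| Threshold, reference days, k | μ | φ without / with offset | Rejection without / with offset |
|---|---|---|---|
| <70, 30, 1.59 (55% with any event) | 1.887 | 5.02 / 4.63 | 0.382 / 0.362 |
| <70, 10, 3.0 (60% with any event) | 5.661 | 22.7 / 21.5 | 0.681 / 0.673 |
| <54, 30, 1.59 | 0.838 | 2.78 / 2.61 | 0.240 / 0.225 |
| <54, 10, 3.0 | 2.513 | 10.6 / 10.1 | 0.548 / 0.538 |

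Simulation in the settings near 60% incidence gave 38-72% for <70. Over all nine combinations of reference days and k, the ranges without and with offset were 30-77% and 25-77% for <70, and 16-64% and 13-63% for <54. With no variation between residents at all (stay of 7 days plus an exponential, capped at 60), Poisson rejected 11.5% without and 4.2% with offset. The offset therefore removes only the part due to unequal stay.

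**Negative binomial without offset, balanced stay.** Error is about 5% in the settings near 60% (5-8% over the grid). The offset adds about 3-4 power points there. Over the grid it adds 1-4 points at a ratio of 0.40 and 0-9 at 0.60; with the exponential stay, power at 0.60 rose from 38% to 48%. For <54 at the hospital contrast (0.08 against 0.75), power is 98-100% either way.

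**Negative binomial, unequal time.** Estimated ratio = true ratio × (mean time, intervention / mean time, control). A true 0.67/1.69 = 0.40 reads 0.40/0.90 = 0.44 if control wear is 10% lower, and 0.40/0.75 = 0.53 if 25% lower. With no effect and one arm's stay multiplied by 1.25 or 1.5 (capped, means 40.2 or 44.6 days against 33.5), error is about 10-15% without offset near 60% incidence, and 4-6% with it. The chance SE of the stay gap is √(2 × 234.1/50) = 3.1 days, so gaps of 6.7 and 11.1 days would need a systematic cause.

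**The offset's own assumption.** If the event rate decays on a 10-day scale (assumed) and one arm stays 1.5 times as long, the offset model rejects a true null in about 10-13% of trials, against 5-6% without offset.

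**Selection.** With n = 100, treatment forced in and 6 or 15 candidates, linear-model false positives were 5.3-6.2% with selection and 4.2-5.0% with fixed covariates. Forward, backward and stepwise chose different sets in 20-68% of runs, but the treatment verdict differed in only 0.3-5%.

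**The case against.** **Role of the count model.** The first comparison and the sample size rest on proportions, and event number is a secondary outcome. This stands. A reader might infer that the main comparison or the 70 per group is undermined; neither uses the count model.

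**The plan already allows the better model.** Negative binomial is named and an offset is not excluded. True, but nothing commits to either.

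**Balance.** Randomisation should balance stay, and the linagliptin trial in long-term care (Section 3) found no significant difference in length of stay between its arms. This stands. A reader might infer that the count result will be biased because control residents wear blinded sensors with alarms off, so that lost sensors go unnoticed. The documents report no wear data by arm, so that is conjecture.

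**Estimand.** Events per stay is a coherent randomised comparison, and the cited trial reports events per patient. The offset is not neutral either: Section 6 adjusts insulin daily and after low values, so early clustering is plausible. This stands, and is why both versions should be reported.

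**Source of events.** The paragraph opens by mentioning POC and CGM, and Section 15 defines events by either. That covers the definition, but the count sentence does not say which is counted. Scheduled POC testing differs by arm (before meals and at bedtime against once daily, Section 6), which no time offset would correct.

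**Selection.** Its effect on error is small, and it concerns models that follow unadjusted tests. Conceded; the case is pre-specification.

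**Conclusion.** The point holds and should be fixed in wording.

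- **Main problem: plain Poisson is permitted.** With 50 per arm and incidence near 60%, it rejects a true null for events <70 in about 38-72% of trials with balanced stay. For <54, the threshold in the unadjusted count model, the same settings give about 24-55% by the formula. These figures depend on the assumed dispersion, reference period and stay. The quoted confidence intervals make overdispersion plausible but do not fix its size. It would be wrong to infer that an offset alone solves this.
- **Smaller problem: no exposure term.** With balanced stay the cost is roughly 3-4 power points (up to about 10 in other scenarios), with error near 5% under negative binomial. Bias in the per-time ratio needs unequal observed time, a risk the documents do not show to be expected.
- **Minor problem: automatic selection.** About 5-6% error against 4-5%. It would be wrong to infer a serious inflation.

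**What to change.** In Section 18, safety analysis:
- Specify negative binomial regression, not plain Poisson, of CGM-detected episodes below 70 and below 54 mg/dL in both arms, with log(valid CGM wear time) as offset and centre in the model.
- Report events per stay, without offset, as a sensitivity analysis.
- Keep the proportion with at least one episode as the first comparison.

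In Section 18, multivariable models: replace selection with the covariates already given as examples (age, gender, BMI, centre, admission HbA1c), with treatment always in the model.

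The cost is plan wording and one derived variable, since both arms wear CGM. Downsides: valid wear time must be defined; the offset assumes that events accrue in proportion to wear time; and fixing six covariate terms cost about 2-3 power points against selection in the linear runs (67-68% against 69-71%), partly because selection rejects slightly too often.

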### **Significance and Innovation.**

**Significance.** Two previous RCTs in the subacute and LTC facilities comparing oral agents and basal insulin reported similar improvement in glycemic control, but high rates of hypoglycemia in patients treated with basal insulin . The rate of hypoglycemia in insulin and sulfonylureas treated patients was 30-40%. Patients with hypoglycemia required greater resource utilization and higher emergency room and hospital transfers compared to residents without hypoglycemia . The high rate of insulin-associated hypoglycemia is worrisome, as recent population studies have suggested that diabetes prescribing in LTC is shifting towards insulin, accounting for ~half of patients with T2D  and nearly 68% of new drug starts . Capillary POC glucose testing is the standard of care for glucose monitoring in the hospital and LTC facilities. Our group and others have shown that POC misses about 40% of hypoglycemia cases, particularly at night (REF). Increased detection of both hypo- and hyper- glycemic events have reported with the use of CGM compare to the POC BG . In addition, we recently reported that CGM-GTS with alarm can successfully reduce the frequency and time in hypoglycemia compared in insulin treated patients with T2D compared to POC (REF). We anticipate that by Reducing hypoglycemia in subacute and long-term skilled nursing care facilities may reduce the rate of complications, ER visits and need for hospital readmissions.

[figure not shown]
**Innovation.** We propose the first RCT to assess the impact of glucose control and hypoglycemia reduction with the use of real time CGM with an alarm system to prevent hypoglycemia and facilitate the care of insulin and non-insulin treated patients with T2D in subacute and long-term skilled nursing care facilities. The results of this study have great potential to impact and facilitate care and to change current clinical guidelines in the management of older adults with diabetes in subacute and LTC facilities.

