**DPP4-inhibitors vs Basal insulin in LTC (Linagliptin-LTC Trial).** A 6-month open-label pilot randomized controlled trial compared the efficacy and safety of a DPP4-i (linagliptin) and basal insulin in subacute and LTC residents with T2D admitted to 3 institutions affiliated with Emory University. A total of 140 residents with T2D treated with oral antidiabetic agents or low-dose insulin (0.1 U/kg/d), with fasting BG>180 mg/dL and/or HbA1c >7.5% were randomized to linagliptin 5 mg day or glargin at a starting dose of 0.1 U/kg/d. Baseline antidiabetic therapy, except metformin, was discontinued on trial entry. BG was measured before meals and both groups received supplemental rapid-acting insulin before meals for BG > 200 mg/dL. As shown in Figure 4, treatment with linagliptin resulted in no significant differences in mean daily BG, but resulted in fewer mild hypoglycemic events <70 mg/dL (3% vs. 37%, P <0.001), and a non-significant trend towards lower risk of BG <54 mg/dL (0% vs 7%, p=0.06). There were no significant between-group differences in length of stay, complications, emergency department visits, or hospitalizations. These results suggested that DPP4-inhibitors are effective and represent an alternative to insulin therapy in many LTC residents with T2D.

**Continuous glucose monitoring (CGM) in the hospital setting.** Our research team have reported on 3 RCTs comparing the accuracy of using of CGM and capillary point of care (POC) glucose testing in insulin treated patients with T2D. Increased detection of both hypo- and hyper-glycemic events with the use of CGM compared to POC testing was found. More than 50% of the hypoglycemic occurred at night; suggesting that many of these episodes would be missed by standard POC testing. In a recent study, we compared the performance of the FreeStyle Libre Pro CGM and POC glucose testing among insulin-treated hospitalized patients with T2D. The mean daily glucose was higher by POC testing, and proportions of patients with BG <70 mg/dl and <54 mg/dl by POC BG were lower compared to CGM, all p<0.001 (Fig 3). The overall mean absolute relative difference (MARD), the statistical measure of accuracy used as the standard in glucose monitoring to represent performance, was 14.8%, ranging between 11.4 to 16.7% for glucoses between 70 and 250 mg/dl and the Error Grid analysis showed 98.0% of glucose pairs within Zones A and B.

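### The 60% versus 35% contrast that sizes the hypoglycemia endpoint has no documented basis as a CGM-GTS effect, and text and table give the 35% to opposite arms

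*Combined protocol and SAP*

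**What the plan says.** The sizing argument is in Section 18, under the data management and statistical analysis text.

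- **Upper rate.** A hospital comparison of two glargine formulations is cited, in which "56% had CGM BG readings <70 mg/dl (vs 14% with POC testing-standard of care". From this the plan concludes that "it is reasonable to assume 60% of resident on LTC facilities will experience one or more BG < 70 mg/dl by CGM".
- **Lower rate.** The next sentence reads "If we assume that 35% in the standard of care group will have at least one BG <70 mg/dl (based on linagliptin LTC study", and 70 patients per group are said to give 80% power with a one-sided t-test.
- **Table.** The row holding 30%, 35%, 40%, 45% and 50% is labelled "Hypoglycemia incidence, Rate in the CGM intervention group". The sample sizes beneath are 49, 70, 107, 186 and 407 per group.
- **Source of the 35%.** Section 3 (Preliminary Results) describes the linagliptin trial as a drug comparison in long-term care. There "BG was measured before meals and both groups received supplemental rapid-acting insulin before meals", and linagliptin gave "fewer mild hypoglycemic events <70 mg/dL (3% vs. 37%, P <0.001" than glargine.
- **CGM-GTS effect.** Just before the calculation, Section 18 quotes 0.67 versus 1.69 episodes per patient (95% CI 0.34-1.30 and 1.11-2.58) for CGM-GTS versus fingerstick care. Section 3 says the controls in that trial wore blinded CGM.
- **This trial.** Sections 6 and 18 put CGM on both arms, blinded in control. Section 18 compares the proportion with hypoglycemia by both methods and names neither as primary. Section 12 sets accrual at 100.

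**The concern.** A sample size for a two-arm comparison needs the outcome rate in each arm, measured in the same way, with the difference attributable to the intervention. Here the two rates come from studies that differ in setting, population, treatment and detection method, and neither is described as using CGM-GTS. Read literally, the sentence also gives the control arm the lower rate, which would make the intervention look harmful. Correcting that label would still leave the intervention rate cited to a trial without the intervention.

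This is the only sizing basis for the hypoglycemia endpoint, so a reader relying on the 80% figure has nothing in the documents to support the effect behind it.

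**Working it through.** **1. Reproduce the plan's figure.** For two proportions, two-sided 0.05, 80% power, with p̄ the mean of p1 and p2 and d = |p1 - p2|:

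n0 = [1.96 √(2p̄(1-p̄)) + 0.842 √(p1(1-p1) + p2(1-p2))]² / d²; with continuity correction, n = (n0/4)[1 + √(1 + 4/(n0 d))]².

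At 0.60 versus 0.35: n0 = (1.384 + 0.575)²/0.0625 = 61.4, and n = 69.2, so 70. The five table columns come out at 49, 70, 107, 186 and 408 (stated: 407). One-sided 0.025 gives the same numbers. One-sided 0.05 does not: it gives 49 for the 35% column, or 56 with correction.

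**2. Which arm holds the 35%?** With 35% as comparator, intervention rates of 30%, 40%, 45% and 50% would need 1417, 1511, 396 and 183 per group, against the table's 49, 107, 186 and 407. The table therefore uses 60% for control and 30-50% for CGM-GTS. The sentence contradicts it.

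**3. Power at the planned accrual on the plan's own rates.** Assume 1:1 allocation, so 50 per arm (the ratio is not stated). Then (0.25√50 - 1.384)/0.684 = 0.56, which is 71% power. With continuity correction the effective n is (50 × 0.25 - 1)²/(50 × 0.25²) = 42.3, which gives 64%.

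**4. Lower rate from the cited CGM-GTS effect.** Ratio = 0.67/1.69 = 0.40. Assume negative binomial counts with dispersion k (k = 0 is Poisson), so P(at least one event) = 1 - (1 + kμ)^(-1/k). Solve for the control mean μ that gives 60%, multiply it by 0.396, and convert back. For example, at k = 1, μ = 1.5, the CGM-GTS mean is 0.595, and 1 - 1/1.595 = 37%.

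For event counts, the variance of the log rate ratio is [(1/μ + k) + (1/(0.396μ) + k)]/50, and power = Φ(|ln 0.396|/SE - 1.96).

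| k | Control mean | CGM-GTS rate | N per arm (corrected) | Power at 50 per arm | Same, corrected | Power, event count <70 mg/dl |
|---|---|---|---|---|---|---|
| 0 | 0.92 | 30% | 50 | 85% | 80% | 92% |
| 0.65 | 1.25 | 35% | 70 | 71% | 64% | 90% |
| 1 | 1.50 | 37% | 84 | 63% | 55% | 88% |
| 1.2 | 1.67 | 39% | 94 | 57% | 49% | 87% |
| 2 | 2.6 | 43% | 147 | 40% | 32% | 81% |
| 3 | 4.9 | 47% | 253 | 25% | 19% | 71% |

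**5. Which k?** The documents give none. If the quoted control mean of 1.69 is also to produce 60%, k is about 1.2: 1 - (1 + 1.2 × 1.69)^(-1/1.2) = 60%. Values of 2 to 3 need control means of 2.6 to 4.9 events, which longer follow-up would have to justify.

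**The case against.** The table does assume an intervention effect, and 70 per group follows from it. It also shows a sensitivity range from 49 to 407. So a reader who inferred that the sizing contains no treatment effect would be going too far: the effect is assumed but unsourced, and the sentence mislabels it.

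A reader might also infer that the 25-point gap is simply what fingersticks fail to detect. Section 3 says "Our group and others have shown that POC misses about 40% of hypoglycemia cases", and 60% × 0.60 = 36%, close to the 35%. The documents do not support that reading. The Section 3 statement has an unfilled reference and does not say whether cases are patients or events. The study behind the 60% gives its own detection gap, 56% by CGM versus 14% by fingerstick, and 60% × 14/56 = 15%, not 36%. The two rates also differ in setting, population and treatment, so this is a mixed-source contrast.

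Nor is 35% refuted. It follows from the cited ratio at k of about 0.65. At the k suggested by the quoted control mean it looks optimistic.

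Finally, the proposed derivation brings in its own unknown, k, and carries a hospital rate ratio into stays of up to 60 days. That objection stands, which is why the result should be shown as a range. The gap between 70 per group and a total of 100 is a separate inconsistency; it enters here only because power has to be stated at some size.

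**Conclusion.** The concern holds: the sizing sentence is wrong as written, and the contrast has no documented basis as an effect of CGM-GTS. What is established is that both cited sources lack the intervention, that text and table disagree on the arm, and that the one relevant effect in the documents is not used. On the plan's own rates, the power available at the planned accrual falls short of the stated 80%.

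The documents do not establish that the trial is underpowered for a true effect. On the cited ratio, power for the any-event proportion runs from adequate to poor depending on dispersion, and the value most consistent with the quoted control mean gives about 57%. These figures rest on a 60% control rate by CGM, a negative binomial count model, transfer of the hospital ratio to long-term care, and 1:1 allocation.

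**What to change.** In Section 18:

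1. State that the sizing comparison uses CGM-detected hypoglycemia in both arms, with control at 60%.
2. Correct the sentence so that the lower rate belongs to CGM-GTS, in line with the table.
3. Replace the linagliptin-trial citation with a rate derived from 0.67/1.69 under a stated k, shown as a range. Justify any k that implies a control mean well above 1.69.
4. Restate power at the planned total of 100, giving the allocation ratio, the test, the alpha level and whether a continuity correction is used.
5. Optionally, report power for the count of events below 70 mg/dl beside it, since the cited effect was measured on that scale. Note that the univariate count model in Section 18 is for clinically significant events, which Sections 4 and 15 define as below 54 mg/dl, while the number of events below 70 mg/dl is a secondary outcome in Section 4.

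The cost is protocol and SAP wording. The stated power for the any-event proportion becomes less favourable. No extra patients are needed.
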